18-Dec-2018	Update the following points : 
 - Added search criteria for comorbidities and RAASi - Updated sensitivity analyses for Central lab assay change for S-K - Updated sensitivity analyses for iSTAT potassium - Added subgroup analyse of S-K and AEs - Updated the summary of exposure - Added analysis of RAASi dose change as per protocol amendment - Added analysis of Questionnaire for QOD or QD regimen - Added Adverse events of special interest - Clarified “on-treatment” definition, especially for under QOD regimen - Added detail of an approach to IA
5-Feb-2019	Update the following points : 
 - Clarified visit aping rule for unscheduled visit - Age/weight cut-offs were updated - Deleted summary for days per dose period for which interpretation is difficult - Added subgroup evaluation for S-K and AEs - Added < 2.5 mmol/L category for hypokalemia summary - Updated compliance calculation to provide more precise value
17-Jun-2019	-Added clarification for the visit mapping and for number of normokalemic days derivation. -Removed descriptive summary of 3-component summary scores for SF36v2, and clarified that scoring will be done based on the standard algorithm.

1. STUDY DETAILS

1.1 Study objectives

Primary Objective:	Outcome Measure:
Maintenance Phase To assess open-label, long-term (12 months) safety and tolerability for ZS in Japanese subjects with hyperkalemia (serum potassium ≥ 5.1 mmol/L).	Safety and tolerability as measured by adverse events reporting, vital signs, ECGs, physical examinations, and safety laboratory measurements.

Secondary Objectives:	Outcome Measures:
Maintenance Phase 
 To evaluate the proportion of ZS-treated subjects in whom normokalemia can be maintained over prolonged periods of time, using an individually titrated dose (5 g every other day [or 2.5 g once daily], 5 g once daily, 10 g once daily or 15 g once daily) To explore the time course of S-Aldosterone and S-Bicarbonate 	
 Proportion of patients who can maintain normokalemia (defined as S-K level of ≥ 3.5 and ≤ 5.0 mmol/L, inclusive) on ZS at each Maintenance Phase study visit Proportion of patients with average S-K ≤ 5.1 mmol/L Proportion of patients with average S-K ≤ 5.5 mmol/L Proportions of patients who were normokalemic (S-K ≥ 3.5 and ≤ 5.0 mmol/L), hypokalemic (< 3.5 mmol/L), or hyperkalemic (> 5.0 mmol/L) at each Maintenance Phase visit. Subject-level average S-K over certain period of time Observed values at visit and change from baseline in S-K over time Number of normokalemic days during Maintenance Phase Change in S-K level from the last on-treatment Maintenance Phase visit to the End of Study (EOS) Change from baseline in S-Aldosterone over time Proportion of patients with normal S-Aldosterone Change from baseline in S-Bicarbonate Proportion of patients with normal S-Bicarbonate

Secondary Objectives:	Outcome Measures:

 To evaluate the health state in the study population using SF-36 v2. 	
 SF-36 v2 questionnaire

Correction Phase To assess efficacy, safety and tolerability of 10 g TID ZS in Japanese patients with hyperkalemia (serum potassium [S-K] \geq 5.1 mmol/L).
	
 Observed values and change from Correction Phase baseline in S-K Proportion of patients who achieved normokalemia at 24, 48 and 72 hours after start of dosing Safety and tolerability as measured by adverse events reporting, vital signs, ECGs, physical examinations, and safety laboratory measurements during Correction Phase

Exploratory Objective:	Outcome Measure:

Maintenance Phase Patient reported outcomes: To evaluate if patients prefer ZS QOD or OD using the patient questionnaire.
	Patient questionnaire

Treatment period To explore change in doses and reasonings of the change of RAAS inhibitors during the treatment period.
	
 Proportion of subjects increased RAASi doses Proportion of subjects who decrease or discontinued RAASi doses Proportion of subjects who increased at least once RAASi due to each reason Proportion of subjects who decreased/discontinued at least once RAASi due to each reason Time to first reduction/discontinuation of RAASi

1.2 Study design

The study is an open label, single arm study with flexible dose regimen focused on assessing long-term safety and tolerability of ZS in Japanese subjects with hyperkalemia.

Correction Phase: If the subject is normokalemic (i-STAT [A portable blood analyser] potassium between 3.5 and 5.0 mmol/L, inclusive) on the morning of Correction Phase Study Day 2 after 3 doses of ZS 10 g, they will enter the Maintenance Phase. If the subject is not normokalemic, they will receive an additional 24 hours of ZS 10 g TID treatment (6 total doses). If the subject's i-STAT potassium value is between 3.5 and 5.0 mmol/L, inclusive, on the morning of Correction Phase Study Day 3, the subject will enter the Maintenance Phase. If the subject is not normokalemic, they will receive an additional 24 hours of ZS 10 g TID

treatment (9 total doses). If the subject's i-STAT potassium value is between 3.5 and 5.0 mmol/L, inclusive, on the morning of Correction Phase Study Day 4, the subject will enter the Maintenance Phase. If the i-STAT potassium value is still < 3.5 mmol/L or ≥ 5.1 mmol/L on the morning of Correction Phase Study Day 4, after 72 hours of TID treatment, the subject will be withdrawn from the study and referred to their normal health care provider for standard of care treatment. Subjects withdrawn from the Correction Phase of the study will return to the clinic 7 (± 1) days after their last dose of ZS for an End of Study (EOS) visit.

Maintenance Phase: Patients will initially be dosed with ZS at a starting dose of 5g QD. During the Maintenance Phase, the ZS dose may be increased up to 15 g QD or decreased down to 5g QOD (or 2.5 g QD) based on i-STAT potassium measurements as outlined in [Table 1](#).

Table 1 Dose Adjustment during MP

Current dose	i-STAT Potassium Value (mmol/L)	Dose Adjustment
5g QOD or 2.5 g QD	≤ 2.9	Discontinue dosing
	3.0-3.4	Discontinue dosing
	3.5-5.0	No change
	5.1-6.5	5g QD
	>6.5	Discontinue dosing
5g QD	≤ 2.9	Discontinue dosing
	3.0-3.4	5g QOD or 2.5 g QD
	3.5-5.0	No change
	5.1-6.5	10g QD
	>6.5	Discontinue dosing
10g QD	≤ 2.9	Discontinue dosing
	3.0-3.4	5g QD
	3.5-5.0	No change
	5.1-6.5	15g QD
	>6.5	Discontinue dosing
15g QD	≤ 2.9	Discontinue dosing
	3.0-3.4	10g QD
	3.5-6.5	No change
	>6.5	Discontinue dosing

Throughout all phases of the study, most potassium values will be measured at fasting before taking ZS. Nothing should be taken by mouth except water, coffee or tea, with or without milk and/or sugar, and essential medications, for a minimum of 8 hours prior to the blood collection. Potassium level should be determined by both i-STAT and the Central Laboratory on all occasions. Treatment decisions (eg, dose titration, stopping rules) will be made based on

i-STAT potassium values, as these provide clinical sites with a real-time measurement, according to dose modification rules. Statistical analyses on the study data will in principle be based on S-K values as measured by the Central Laboratory.

Safety and tolerability will be assessed on an ongoing basis. Standard study assessments including blood potassium, clinical chemistry (including calcium, magnesium, sodium, phosphate, creatinine, bicarbonate, and blood urea nitrogen [BUN]), aldosterone, renin and hematology parameters, urinalysis, vital signs, physical examinations, and electrocardiograms (ECGs) will be assessed. All women of childbearing potential will have a urine pregnancy test prior to enrollment and at their End of Study (EOS) visit.

Stopping rules will be implemented to ensure subjects discontinue the study treatment and receive alternative therapy in case of significant hyperkalemia, hypokalemia, arrhythmias, or development of congestive heart failure or end stage renal failure.

1.3 Number of subjects

Sample size of in total 150 subjects to be enrolled to this study was determined so that at least safety data of 100 subjects treated by ZS as long as one year will be collected, assuming 35% drop out rate.

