2.1.1 Enrolled subjects

All subjects who signed informed consent.

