4.1.1 Objectives and hypotheses

The objectives of this study is to assessing the safety, tolerability and efficacy of long-term treatment up to 52 weeks with ZS flexible dose regimen (starting with 5g QD, up-/down-titration between 2.5g QD (5g QOD) and 15g QD). There are no confirmatory statistical testing in this study and all analyses will be interpreted in a descriptive manner.

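### SAP section 1.3: 150 subjects at 35% drop-out give 97.5 expected one-year subjects, slightly short of the stated minimum of 100

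*SAP*

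**What the plan says.** SAP section 1.3 is a single sentence. It fixes the size, "Sample size of in total 150 subjects to be enrolled to this study", and gives the aim together with its one assumption: "at least safety data of 100 subjects treated by ZS as long as one year will be collected, assuming 35% drop out rate".

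The SAP gives no other basis for the number of subjects. Section 4.1.1 says: "There are no confirmatory statistical testing in this study and all analyses will be interpreted in a descriptive manner". There is therefore no power or precision calculation beside the exposure count.

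Section 1.3 does not say whether the 35% is a rounded figure, or from which point in the study it is counted.

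**The concern.** The three numbers in the sentence do not fit together as written. Taking 35% away from 150 leaves fewer than 100, while the sentence presents 100 as a minimum. The two round figures, 150 and 35%, both sit on the unfavourable side of what the target needs.

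Little is at stake, but not nothing. The primary objective in section 1.1 is safety and tolerability over 12 months, and the number of subjects observed for a year is the only reason given for the trial's size. Anyone who later compares the one-year exposure achieved with section 1.3 will use a benchmark that the plan's own assumption does not quite support. A study that ran exactly as assumed would seem to have fallen short.

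**Working it through.** **Inputs, all from SAP section 1.3**

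- Planned enrolment: N = 150
- Assumed drop-out: d = 0.35
- Target with one year of safety data: at least 100

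**Step 1. Reproduce the plan's figure.** The usual inflation is target / (1 − d):

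100 / (1 − 0.35) = 100 / 0.65 = 153.8, rounded up to 154.

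The SAP has 150, which is 4 fewer (4/150 = 2.7%). So 150 is close to the right answer and is recognisable as a rounded version of it. The common wrong inflation, target × (1 + d) = 100 × 1.35 = 135, does not give 150, so there is no sign of a wrong formula.

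**Step 2. Expected yield from the stated enrolment.**

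N × (1 − d) = 150 × 0.65 = 97.5.

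Shortfall: 100 − 97.5 = 2.5 subjects, or 2.5% of the target.

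**Step 3. Drop-out at which 150 would be enough.**

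1 − 100/150 = 0.333, so 33.3%. At that rate 150 gives exactly 100 in expectation.

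**Step 4. Chance of reaching 100, for context only.** This step adds an assumption that the SAP does not make: each subject completes independently with probability 0.65.

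| Enrolled | Expected with one-year data | P(100 or more) | P(fewer than 100) |
|---|---|---|---|
| 150 (as stated) | 97.5 | 0.37 | 0.63 |
| 154 (exact inflation) | 154 × 0.65 = 100.1 | 0.54 | 0.46 |

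The two rows have to be read together. Planning on an expected count leaves a chance near one half of falling below it, even when the inflation is exact. Using 150 instead of 154 costs about 17 percentage points (0.54 against 0.37).

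**The case against.** The strongest reply is that this is rounding. 150 is within 3% of the exact 154, and a drop-out of one third, which is near 35%, makes the sentence exactly right. Planning on an expected count is the ordinary reading of a drop-out inflation. No test, error rate or analysis set depends on whether the figure is 97.5 or 100. Section 4.2.3.1 already reports subjects by duration of exposure, with a category above 360 days, and total subject-years. The exposure achieved will therefore be visible whatever section 1.3 says.

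Most of this stands, and it is why the point is minor. It does not make the sentence correct. Section 1.3 states a floor rather than an approximate figure, the rounding goes in the direction that misses the floor, and nothing elsewhere in the SAP repairs it.

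A reader might infer something stronger in three ways, none of which the document supports.

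- *The target will be missed about 63% of the time.* Section 1.3 attaches no probability to reaching 100. Most of the 63% comes from planning on an expectation, since 154 subjects would still miss about 46% of the time. The figure also needs independent drop-out, which the SAP does not specify.
- *Correction Phase withdrawals come off before the 35%, so the yield is lower still.* Section 1.3 attaches the 35% to the 150 enrolled and does not limit it to the Maintenance Phase. It may already cover those withdrawals, so taking them off first risks counting them twice. The SAP gives no share entering the Maintenance Phase from which to compute a further loss.
- *The 150 includes screen failures, because section 2.1.1 defines enrolled subjects as* "All subjects who signed informed consent". That definition names a set used for disposition reporting. Section 1.2 places a pregnancy test before enrolment, which suggests a later point. The meaning in section 1.3 is not fixed, and if 150 did count consented subjects, the 35% could cover screen failures too. Equally, the SAP does not establish that 150 means dosed subjects.

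**Conclusion.** The point holds as a small numerical inconsistency in the sample-size sentence. On its stated inputs, section 1.3 gives 97.5 expected subjects with one year of data against a promised minimum of 100: a shortfall of 2.5 subjects, or 2.5%. Closing it on paper takes 154 subjects or a drop-out of at most 33.3%.

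This rests only on section 1.3 and on applying the 35% once to all 150. It does not depend on the binomial calculation or on any view of who counts as enrolled.

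It would be too strong to say that the trial's size is unjustified or that the design fails. The gap is consistent with rounding, and no power, error rate or analysis is affected. It merits a correction because the sentence is the sole stated basis for the size, and the correction is almost free.

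**What to change.** Reword the sentence in SAP section 1.3 and leave the enrolment figure alone. Either of these is consistent with the arithmetic:

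- *150 subjects with 35% drop-out are expected to give about 97 subjects with one-year data*; or
- *about 100 subjects with one-year data are expected if drop-out does not exceed 33%*.

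The sponsor should choose whichever matches the assumption actually used in planning. If a probability of reaching 100 is quoted, give the 37% for 150 beside the 54% for 154 and state the independence assumption.

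The cost is one sentence. The stated expectation becomes slightly less favourable, or the drop-out assumption slightly more optimistic. No patients are added and no analysis changes.

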2. ANALYSIS SETS

2.1 Definition of analysis sets

Efficacy and safety analysis sets will be defined for each of correction phase and maintenance treatment phase.

2.1.1 Enrolled subjects

All subjects who signed informed consent.

2.1.2 Full analysis sets

All efficacy analyses will be performed using an Intent-to-Treat (ITT) principle based on the full analysis sets.

FAS-CP : For the correction phase (CP), the full analysis set will include all patients that receive at least one dose of ZS during the correction phase and have any post-baseline correction phase S-K values.

FAS-MP : For the subsequent long-term maintenance phase (MP), the full analysis set will include all patients who receive at least one dose of ZS during maintenance phase and have any post-baseline maintenance phase S-K values.

2.1.3 Safety analysis sets

SAF-CP: For the correction phase, the safety analysis set will include all patients treated with at least one dose of correction phase ZS and had any correction phase safety data.

SAF-MP: For the subsequent long-term maintenance phase, the safety analysis set will include all patients treated with at least one dose of maintenance phase ZS and had any maintenance phase safety data.

2.2 Protocol deviations

Protocol deviations will be identified programmatically or manually prior to database lock. Subjects who deviate from important protocol conditions (e.g. selected inclusion/exclusion criteria) will be reported as having important protocol deviations.

Important protocol deviations would include but not limited to:

- Patients who received ZS but did not meet Inclusion/Exclusion criteria
- Patients who received prohibited concomitant medication or non-drug therapy
- Patients who received wrong ZS dose regimen (including incorrect up-/down-titration)
- Study drug compliance < 80% or > 120%.

No protocol deviations will lead to exclude subjects from analysis. All the efficacy analyses will be based on the FAS and all the safety analyses will be based on SAF for each phase.

3. PRIMARY AND SECONDARY VARIABLES

3.1 Primary variables (Safety)

Safety and tolerability of long-term ZS treatment (starting with 5g QD, flexible titration between 2.5g QD (5g QOD) and 15g QD) in patients with hyperkalemia will be evaluated by the following safety measures :

- Adverse Events (AEs)
- Safety clinical laboratory assessments
- Vital signs
- ECGs

3.2 Secondary variables

3.2.1 Efficacy in Maintenance phase

Efficacy of long-term ZS treatment in patients with hyperkalemia will be evaluated by the following efficacy measures:

- Proportion of patients who can maintain normokalemia (defined as S-K level of ≥ 3.5 and ≤ 5.0 mmol/L, inclusive) on ZS at each Maintenance Phase study visit
- Proportion of patients with average S-K ≤ 5.1 mmol/L
- Proportion of patients with average S-K ≤ 5.5 mmol/L
- Proportions of patients who were normokalemic (S-K ≥ 3.5 and ≤ 5.0 mmol/L), hypokalemic (< 3.5 mmol/L), or hyperkalemic (> 5.0 mmol/L) at each Maintenance Phase visit.
- Subject-level average S-K over the certain period of time (as specified below)
 - entire MP [Day 2 to Day 362]
 - Month 3 to Month 12 [Day 82 to Day 362]
 - Day 2 to Month 3 [Day 2 to Day 82]
 - Month 4 to Month 6 [Day 110 to Day 166]
 - Month 7 to Month 9 [Day 194 to Day 278]
 - Month 10 to Month 12 [Day 306 to Day 362]
- Observed values at visit and change from baseline in S-K over time up to Week 52 [Day 362]
- Number of normokalemic days during Maintenance Phase
- Change in S-K level from the last on-treatment Maintenance Phase visit to the End of Study
- Change from baseline in S-Aldosterone over time
- Proportion of patients with normal S-Aldosterone
- Change from baseline in S-Bicarbonate over time
- Proportion of patients with normal S-Bicarbonate
- SF-36 v2 questionnaire

3.2.2 Efficacy in Correction Phase

Efficacy in the Correction Phase ZS treatment in patients with hyperkalemia will be evaluated by the following efficacy measures:

- Observed values and change from Correction Phase baseline in S-K through to 72 hours
- Proportion (and cumulative proportion) of patients who achieved normokalemia at 24, 48 and 72 hours after start of dosing

3.2.3 Safety in Correction Phase

Safety in the Correction Phase ZS treatment will be evaluated by the same variables as described in section 3.1.

3.3 Exploratory variables

- Patient questionnaire
- Proportion of subjects increased RAASi doses
- Proportion of subjects who decrease or discontinued RAASi doses
- Proportion of subjects who increased at least once RAASi due to each reason
- Proportion of subjects who decreased/discontinued at least once RAASi due to each reason
- Time to first reduction/discontinuation of RAASi

4. ANALYSIS METHODS

4.1 General principles

The SAS® software, version 9.2 or higher, will be used in order to generate all the statistical outputs.

Unless otherwise specified, all efficacy analyses will be carried out on the FAS and all safety analyses will be based on the SAF, for each study phase (CP or MP).

4.1.1 Objectives and hypotheses

The objectives of this study is to assessing the safety, tolerability and efficacy of long-term treatment up to 52 weeks with ZS flexible dose regimen (starting with 5g QD, up-/down-titration between 2.5g QD (5g QOD) and 15g QD). There are no confirmatory statistical testing in this study and all analyses will be interpreted in a descriptive manner.

4.1.2 Definitions

4.1.2.1 Baseline Value

For S-K, Correction Phase (CP) baseline value will be established by the mean of 2 different S-K values, recorded 60 minutes apart (to confirm qualification for study entry) on the Correction Phase (CP) Day 1. Maintenance Phase (MP) baseline value will be defined as the measurement taken in the morning of the day of entering maintenance phase (Visit 6, MP Day 1). Note that two types of baseline (CP baseline and MP baseline) are defined only for S-K.

For the other variables (excluding S-K), baseline value of a parameter (eg, safety laboratory test, ECG or vital signs, etc) is defined as the last assessment of that parameter immediately prior to the start of the first dose of ZS during the Correction Phase. Typically, the baseline refers to the measurements obtained within 1 day (24 hours) of start of correction phase ZS treatment.

4.1.2.2 Change and Percent Change from Baseline

Change from baseline to any Time (Day or Hour) t in is defined as follows:

$$C_{Time\ t} = M_{Time\ t} - M_{baseline},$$

where:

- $C_{Time\ t}$ is the change from baseline at Time t ,
- $M_{Time\ t}$ is the measurement at Time t ,
- $M_{baseline}$ is the measurement at baseline.

Percent change from baseline to any Time (Day or Hour) t is defined as follows:

$$P_{Time\ t} = 100 \times (M_{Time\ t} - M_{baseline}) / M_{baseline}.$$

Where $P_{Time\ t}$ is the percent change from baseline at Time t , and $M_{Time\ t}$ and $M_{baseline}$ are defined as above.

4.1.3 Visit/Time windows

In principle, analyses will be based on **nominal visit basis**, only if scheduled visit is available. In absence of scheduled visit, the unscheduled visits and discontinuation visit will be mapped according to the below windows and utilized for by-visit analysis (Table 2 and Table 3).

If scheduled visit is missing,

- If an unscheduled visit exists for that visit window, it will be used.
- If two or more unscheduled visits are available for the same window, the one closest to nominal target day will be used.

- If two unscheduled observations are equally close to target day, the last observation will be used.

As outlined in the table, S-K measurement taken within 1 day (2 days on QOD regimen) after last dose will be regarded as on-treatment and used in analysis. Unscheduled S-K measurement taken more than 1 day (2 days on QOD regimen) after last dose of ZS could be mapped to EOS (Follow up) visit.

Table 2 Visit window for correction phase

Study Visit	Nominal Day	Target Day	From	To
1	Screening (CP Baseline)		-	-1
2	CP Day 1 (CP Baseline)	1	1	1
3	CP Day 2	2	2	2
4	CP Day 3	3	3	3
5	CP Day 4	4	4	4
EOS	CP Follow Up	10	5	17

Table 3 Visit window for maintenance phase

Study Visit	Nominal Day	Target Day	From	To*
6	MP Day 1 (MP Baseline)	1	1	1
7	MP Day 2	2	2	3
8	MP Day 5	5	4	8
9	MP Day 12	12	9	15
10	MP Day 19	19	16	22
11	MP Day 26	26	23	39
12	MP Day 54	54	40	67
13	MP Day 82	82	68	95
14	MP Day 110	110	96	123
15	MP Day 138	138	124	151
16	MP Day 166	166	152	179
17	MP Day 194	194	180	207
18	MP Day 222	222	208	235
19	MP Day 250	250	236	263
20	MP Day 278	278	264	291

Study Visit	Nominal Day	Target Day	From	To*
21	MP Day 306	306	292	319
22	MP Day 334	334	320	347
23	MP Day 362	362	348	Last dose + 1 day (2 days, on QOD regimen)
EOS	MP Follow Up	last dose + 7 days	last dose +2 days (+3 days, on QOD regimen)	last dose + 14 days

*S-K measurements more than 1 day (2 days, on QOD regimen) after last dose will be regarded off-treatment and will be mapped to the EOS visit.

Note : Any available measurements regardless of scheduled or unscheduled will be taken into account when summarizing the incidence of certain event based on most extreme (lowest or highest) values in safety evaluation (e.g. analysis of incidence of hypokalemia, etc).

